Because MLN9708 is an investigational agent, it should be handled with due care. Patients should be instructed not to chew, break, or open capsules. In case of contact with broken capsules, raising dust should be avoided during the clean-up operation. The product may be harmful by inhalation, ingestion, or skin absorption. Gloves and

protective clothing should be worn during cleanup and return of broken capsules and powder to minimize skin contact.

The area should be ventilated and the site washed with soap and water after material pick-up is complete. The material should be disposed of as hazardous medical waste in compliance with federal, state, and local regulations.

In case of contact with the powder (e.g. from a broken capsule), skin should be washed immediately with soap and copious amounts of water for at least 15 minutes.

In case of contact with the eyes, copious amounts of water should be used to flush the eyes for at least 15 minutes. Medical personnel should be notified.

9. Statistical Considerations:

The study is a multicenter phase I/II trial evaluating the safety and efficacy of MLN9708 for the prophylaxis of chronic GVHD in patients with hematological malignancies and bone marrow failure syndromes undergoing allogeneic HCT. The primary objectives of this study is to determine the MTD, DLT, RDP, and safety of MLN9708 as chronic GVHD prophylaxis in allogeneic HCT, as well as to evaluate the 1 year cumulative incidence of chronic GVHD patients prophylaxis with MLN9708. During the phase I portion, dose escalation will be carried out according to standard 3+3 design. MTD will be the dose level with ≤ 1 out of six patients developing DLTs. No intrapatient dose escalation will be permitted. Patients undergoing either matched sibling or unrelated donor allogeneic HCT will be eligible for phase I study.

Due to the differences in the incidence rates of chronic GVHD after sibling and unrelated donor transplantation, this study will be designed to accrue these 2 cohorts separately but in parallel, with the null hypothesis of a rate of chronic GVHD at 1-year of 55% after sibling transplantation and 65% after unrelated transplantation. The alternative hypothesis will be a 25% reduction with the use of new treatment in both cohorts. With this hypothesis, using an exact binomial distribution, the probability of

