concluding the new treatment is promising, will be 0.80 (statistical power) when the true but unknown rate of developing chronic GVHD is 30% or 0.04 (type I error) when the true rate is 55% in related donor transplantation (Cohort A [matched sibling donor transplantation] with a sample size of 25). Similarly, the probability of concluding the new treatment is promising, will be 0.81 (statistical power) when the true but unknown rate of developing chronic GVHD is 40% or 0.05 (type I error) when the true rate is 65% in unrelated transplantation (Cohort B [unrelated donor transplantation] with a sample size of 26). The efficacy endpoint is chronic GVHD-free at 1 year and there will be no interim analysis on efficacy for this multi-center study. In the final analysis in Cohort A, if 10 or more of 25 patients have chronic GVHD, we will conclude the new treatment is ineffective in Cohort A; for Cohort B, if 13 or more of 26 patients have chronic GVHD, we will conclude the new treatment is ineffective in Cohort B.

Demographic and baseline laboratory results will be summarized using descriptive statistics, including means with standard deviations, or medians with ranges, histograms and box-plot. The chronic GVHD rate at 1-year and its 95% CI will be calculated by cumulative incidence method, while accounting for competing events. Progression-free survival and overall survival will be estimated using the Kaplan-Meier method.

Cumulative incidence of acute and chronic GVHD, disease relapse and non-relapse mortality will be calculated by accounting for competing events. Competing events for acute GVHD disease are relapse or death without acute GVHD, while those for chronic GVHD are relapse or death without chronic GVHD. Disease relapse and non-relapse mortality are competing events for each other. Toxicity will be reported by type, frequency and severity. Worst toxicity grades per patient will be tabulated for selected adverse events and laboratory measurements. Patients replaced on the protocol (as specified in the Dose Modification Section) will remain evaluable for safety and toxicity assessment.

Safety/Stopping Rules:

For the phase II portion of the study we propose to accrue 51 patients over 24–30 months, which will enroll about 12 patients every 6 month time period. We plan to

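### Cohort B's type I error is 0.038 under the stated exact rule, not 0.05, and both stated powers are off by about 0.01

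*Combined protocol and SAP*

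**What the plan says.** All the inputs are in Section 9, Statistical Considerations.

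- **Method:** the operating characteristics are derived "using an exact binomial distribution", separately in each cohort, with no interim efficacy analysis.
- **Null rates:** "null hypothesis of a rate of chronic GVHD at 1-year of 55% after sibling transplantation and 65% after unrelated transplantation".
- **Alternative:** "The alternative hypothesis will be a 25% reduction with the use of new treatment in both cohorts". The rates that follow in the text are 30% (Cohort A) and 40% (Cohort B), so the reduction is 25 percentage points.
- **Cohort A:** the probability of a promising conclusion "will be 0.80 (statistical power) when the true but unknown rate of developing chronic GVHD is 30% or 0.04 (type I error") at 55%. The rule: "if 10 or more of 25 patients have chronic GVHD, we will conclude the new treatment is ineffective in Cohort A".
- **Cohort B:** the same probability "will be 0.81 (statistical power) when the true but unknown rate of developing chronic GVHD is 40% or 0.05 (type I error") at 65%. The rule: "if 13 or more of 26 patients have chronic GVHD, we will conclude the new treatment is ineffective in Cohort B".

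The size of Cohort B is not the same throughout. The power statement and the decision rule use 26. The Protocol Summary (Number of Patients) and the Accrual Estimate at the end of Section 9 plan to enrol 27 unrelated-donor patients.

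**The concern.** Method, rates, sample sizes and cut-offs are all given, so each error rate can be recomputed without any assumption. Three of the four stated probabilities do not come back to the two decimals printed. The one that matters most is Cohort B's type I error.

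Chronic GVHD at 1 year is the phase II primary objective, and each cohort's conclusion rests on a single count. The type I error and power are what a reader will quote beside that conclusion. If they are wrong, the strength of the evidence is misdescribed even when the rule is applied correctly. They are also the baseline that anyone needs when deciding what to do about 26 versus 27 patients.

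**Working it through.** **Set-up.** Let X be the number of patients with chronic GVHD in a cohort of n. The treatment is called promising if X ≤ c, where c is one less than the count at which the plan declares it ineffective: c = 10 − 1 = 9 for Cohort A and c = 13 − 1 = 12 for Cohort B.

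- Type I error = P(X ≤ c | n, p0) = Σ(k = 0 to c) C(n,k) p0^k (1 − p0)^(n−k)
- Power = the same sum with p1 in place of p0

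**Stated rules, exact binomial:**

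| Cohort | n, c | p0 / p1 | Type I error: stated | exact | Power: stated | exact |
|---|---|---|---|---|---|---|
| A | 25, 9 | 0.55 / 0.30 | 0.04 | 0.0440 | 0.80 | 0.8106 |
| B | 26, 12 | 0.65 / 0.40 | 0.05 | 0.0377 | 0.81 | 0.8007 |

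Cohort A's type I error reproduces. Cohort B's differs by 0.05 − 0.0377 = 0.0123. The powers differ by 0.8106 − 0.80 = 0.0106 (A, understated) and 0.81 − 0.8007 = 0.0093 (B, overstated).

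**Can another reading give Cohort B's 0.05 with 0.81?**

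| Variant for Cohort B | Type I error | Power |
|---|---|---|
| 11 or fewer of 26 | 0.015 | 0.674 |
| 13 or fewer of 26 | 0.083 | 0.892 |
| 12 or fewer of 27 | 0.023 | 0.750 |
| 13 or fewer of 27 | 0.054 | 0.855 |
| 12 or fewer of 25 | 0.060 | 0.846 |
| 11 or fewer of 24 | 0.042 | 0.787 |
| Normal approximation, n = 26, alpha set at 0.05 | 0.05 | 0.841 |
| The same with continuity correction | 0.05 | 0.788 |
| Normal approximation of the stated rule, cut at 12.5 | 0.035 | 0.800 |

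None does. A search over n = 15 to 49 and all cut-offs at 65% versus 40% finds no single-stage exact rule that rounds to both 0.05 and 0.81.

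**Is the reduction meant as relative?** A relative 25% reduction gives 0.55 × 0.75 = 0.4125 and 0.65 × 0.75 = 0.4875, with powers of 0.375 and 0.473. That is far from the stated values, so the absolute reading is the right one.

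**The case against.** **The 0.05 could be a nominal ceiling that the rule respects.** The rule does respect it. But the sentence gives 0.05 as the probability of a promising conclusion when the true rate is 65%, in the same form as Cohort A's 0.04, which is the attained value rounded. Read as a ceiling, the two cohorts would be reported on different bases with no notice to the reader.

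**The impact is small.** This stands. Cohort B's type I error is overstated by 1.2 percentage points, so the rule is stricter than advertised. The power differences are about one point each, and both powers stay at or above 0.80. The decision rules are explicit counts, so corrected probabilities could not change the conclusion in either cohort.

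**Stronger readings that the documents do not support.**

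- A reader might infer that none of the stated error rates follows from the rules. Cohort A's type I error does.
- A reader might infer that the two powers were interchanged, since the exact values round to 0.81 (A) and 0.80 (B), the reverse of the text. Nothing in the plan shows this. A normal approximation at alpha 0.04 also gives 0.796 for Cohort A, and swapping figures between the cohorts would not explain the 0.05, because Cohort A's exact type I error is 0.044.
- A reader might infer that the design is under-powered or fails to control type I error. For the stated rules at 25 and 26 patients it does neither.

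**The correction depends on n = 26.** This also stands. With 27 analysed, neither adjacent cut-off gives the corrected Cohort B figures.

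**Conclusion.** The point holds as a reporting correction of the lowest severity. Under the plan's own method and rule, Cohort B's type I error is 0.038 instead of 0.05. Power is 0.811 instead of 0.80 in Cohort A and 0.801 instead of 0.81 in Cohort B. Cohort A's type I error of 0.04 is right.

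The figures rest on a single-stage, one-sided exact binomial rule, as Section 9 describes it, with exactly 25 and 26 patients analysed. How the stated figures arose cannot be determined from the documents. Cohort B's exact power clears 0.80 by less than 0.001, so the choice between 26 and 27 is not neutral: at 27, keeping 12 or fewer lowers power to 0.750, and moving to 13 or fewer raises type I error to 0.054.

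**What to change.** In Section 9, keep the decision rules and restate the probabilities:

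- Cohort A (25 patients, promising if 9 or fewer have chronic GVHD): power 0.81, type I error 0.04.
- Cohort B (26 patients, promising if 12 or fewer have chronic GVHD): power 0.80, type I error 0.04 (exact 0.038).

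In the same edit, reconcile the 26 in the Cohort B rule with the 27 unrelated-donor patients in the Protocol Summary and the Accrual Estimate. Say how many are analysed under the rule. If it is 27, give the cut-off for 27 with its own figures: type I error 0.023 and power 0.750 for 12 or fewer, or 0.054 and 0.855 for 13 or fewer.

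The cost is the two sentences that hold the error rates, plus a clarification of the Cohort B number. At 26 analysed, no sample size or cut-off changes. Cohort B's stated power falls by one point and Cohort A's rises by one.

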monitor and evaluate short term adverse events at each additional 12 patients who have been enrolled in the study. The expected 100 day post-transplant immunologic graft rejection (defined as less than 5% donor myeloid cells) rate is approximately 2.5% (in absence of relapsed disease) and the enrollment will be put on hold if more than 5% graft rejection rate is seen. For the development of grade 3-4 adverse events deemed to be related to MLN9708, the true rate is 5% and enrollment will be on hold if more than 10% adverse events are observed. The stopping boundaries for graft rejection and development of grade 3-4 adverse events are shown in Table below. In the case of a safety event suspending study, a prompt cumulative examination of all data and circumstances of these events will be conducted by the Medical College of Wisconsin DSMC to determine whether study should be resumed, whether the protocol will be revised or whether the study will be discontinued permanently.

Table. Stopping boundary for adverse events.

Number of patients enrolled	Stopping boundary for immunologic graft-rejection	Stopping boundary for developing grade 3-4 adverse events related to MLN9708
12	≥ 3	≥ 3
24	≥ 3	≥ 4
36	≥ 4	≥ 6
48	≥ 4	≥ 6
51	≥ 5	≥ 7

Accrual Estimate: 6-12 patients will be enrolled in the phase I part of the protocol. In the phase II portion a total of 52 patients (25 sibling and 27 unrelated donor transplantation) will be enrolled, with 1-3 per month. Total estimated accrual = 58 patients.

Accrual Period : Approximately 24-30 months

Follow-Up Period : Two years to evaluate incidence of acute and chronic GVHD and relapse pattern, and five years for survival outcomes.

10. Adverse Event Reporting Requirements

11. Definitions

The following are definitions of adverse events as defined by 21CFR312.32.

Types of Adverse Events

Adverse Event (AE) means any untoward medical occurrence associated with the use of a drug in humans, whether or not consider drug related. An AE can therefore be any unfavorable and unintended sign (including an abnormal laboratory finding), symptom, or disease temporally associated with the use of a medicinal (investigational) product whether or not it is related to the medicinal product. This includes any newly occurring event, or a previous condition that has increased in severity or frequency since the administration of study drug.

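### If a cohort reaches its chronic GVHD limit during accrual, no rule closes enrolment, although its go/no-go verdict is by then fixed

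*Combined protocol and SAP*

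**What the plan says.** Section 9 (Statistical Considerations) sets a single-stage rule for each cohort, applied in the final analysis. For siblings, "if 10 or more of 25 patients have chronic GVHD, we will conclude the new treatment is ineffective in Cohort A"; for unrelated donors, "if 13 or more of 26 patients have chronic GVHD, we will conclude the new treatment is ineffective in Cohort B". The null hypothesis is a "rate of chronic GVHD at 1-year of 55% after sibling transplantation and 65% after unrelated transplantation", and the alternatives are 30% and 40%. The endpoint is worded as follows: "The efficacy endpoint is chronic GVHD-free at 1 year". The objectives speak of 1-year cumulative incidence from the date of HCT. On looks at the data, Section 9 says "there will be no interim analysis on efficacy for this multi-center study".

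The same section gives "Accrual Period : Approximately 24-30 months", about 12 patients per 6 months, and 1–3 per month. Its only enrolment holds are for graft rejection and drug-related grade 3–4 events. The Data Safety Monitoring Plan in Section 5 lets the committee recommend suspension or termination, and Closure of the Study in Section 12 allows discretionary closure. Neither refers to the chronic GVHD count.

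**The concern.** Under a cumulative incidence endpoint, a patient who has had chronic GVHD within 1 year stays a case. The running count can therefore only rise, and once it reaches 10 (A) or 13 (B) no later patient can bring the cohort back to a favourable verdict. Accrual lasts two years or more, and each patient's endpoint is complete about 9–10 months after the first dose, so the limit can be reached with patients still to enrol. The count is knowable at that time: the drug is open-label and GVHD is assessed at scheduled visits.

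Patients enrolled after that point would take an investigational prophylactic agent in a cohort whose go/no-go verdict is settled. Closing enrolment at the limit is curtailment of the existing rule. It adds no threshold and uses no alpha.

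**Working it through.** **1. The plan's own figures.** Let X be the number of chronic GVHD cases. Type I error is P(X ≤ limit − 1) at the null rate, and power is the same probability at the alternative (exact binomial).

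- Cohort A, n = 25, favourable if X ≤ 9: 0.044 at 55% (stated 0.04) and 0.811 at 30% (stated 0.80).
- Cohort B, n = 26, favourable if X ≤ 12: 0.038 at 65% (stated 0.05) and 0.801 at 40% (stated 0.81).

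Cohort B's stated type I error does not follow from its rule. That is a separate matter and does not affect this point.

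**2. Curtailment leaves these unchanged.** If the running count has reached the limit k, the final count is at least k, so the full trial would also give a verdict of ineffective. If it never reaches k, nothing is curtailed. Every trial keeps its verdict, so both error rates stay as computed. This needs two things: any chronic GVHD by 1 year counts, and every case in the running count belongs to the final 25 or 26.

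**3. How often it would matter.** This was simulated with 40,000 trials per setting.

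- From the documents: limits, cohort sizes, null and alternative rates, and dosing from day +60 to +90 (first dose set at day 75). Accrual of 25 patients over 30 months is 25/30 = 0.83 per month. Twelve per 6 months overall is 2 per month, or 1.0 per cohort. Three per month overall is 1.5 per cohort.
- Assumed, because the documents give neither: an even split of accrual between cohorts with random (exponential) gaps, and onset uniform over day 100–365 or day 90–270 after HCT.
- Each case is counted either at onset or at the next scheduled visit (about day 100, 180 or 365, Section 6).

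Results at the null rates, with ranges over the settings:

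| Setting | A: limit reached before last enrolment | A: mean spared | B: limit reached before last enrolment | B: mean spared |
|---|---|---|---|---|
| 0.83–1.0 per month, at onset | 63–80% | 2.7–4.4 | 56–78% | 2.0–3.6 |
| 0.83–1.0 per month, at visits | 41–63% | 1.4–2.7 | 32–55% | 1.0–2.0 |
| 1.5 per month, at visits | 15–27% | 0.4–0.8 | 9–19% | 0.2–0.5 |

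The mean spared includes trials in which nobody is spared. In a trial where the limit is reached during accrual, the number still to enrol is the mean divided by the probability. With onset counting in A this runs from 2.7/0.63 = 4.3 to 4.4/0.80 = 5.5. With visit counting in B it runs from 1.0/0.32 = 3.1 to 2.0/0.55 = 3.6.

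**4. Bounds.** If every outcome were known at once, curtailment would spare 25 − 18.06 = 6.9 patients in A and 26 − 19.94 = 6.1 in B at the null. At the alternatives (30%, 40%) the limit is reached during accrual in 8% of trials or fewer, all of which fail the rule anyway.

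**5. Accrual pace.** The fast end of 1–3 per month means 51/3 = 17 months, which is shorter than the stated 24–30. The slow end means 51 months, which is longer and would raise the percentages. The 24–30 month rows are therefore the best guide, and the 1.5 row is an unfavourable case.

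**The case against.** A single-stage design without an interim efficacy look is a legitimate and explicit choice. Nothing in the documents contradicts it, and no error rate is damaged. That stands: this is an improvement to the design, and the plan is not in error.

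A reader might infer that later patients would be treated for nothing. The documents do not support that. The primary objectives are to determine the 1-year cumulative incidence in each cohort and to assess safety, and the incidence is to be reported with a 95% interval. Later patients inform all of this, and the secondary objectives too. Only the go/no-go verdict is fixed.

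The size also depends on when cases become known. After day 100 the protocol schedules assessments at about days 180 and 365, so counting at onset is optimistic, although unscheduled diagnoses would move the figures back toward it.

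The committee reviews reports twice a year, and the sponsor may close the study under an open list of reasons, so stopping is possible. Nothing requires anyone to look at the count, however, so the gap remains. Exposure is limited to four doses, no DLTs were seen in the six phase I patients, and related grade 3–4 events have their own hold. These facts lower the stakes without removing the point.

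**Conclusion.** The point holds as a cheap improvement. Section 9 lets a cohort go on enrolling after its go/no-go verdict is settled, and no other section ties enrolment to the chronic GVHD count.

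It would be wrong to conclude that each cohort will do so. It is a realistic prospect only if the drug does not work, and rare if it works as hoped. At the null rates and the planned pace, mean savings are about 1 to 4 patients per cohort, and under 1 with fast accrual and visit-based counting. The percentages rest on the assumed onset distributions and the even split of accrual. The statement that verdict, type I error and power are unchanged needs no timing assumption. It does require a clear definition of which patients and which events count.

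**What to change.** Settle three definitions first:

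- Whether patients replaced for missing more than one dose (Section 5) count toward efficacy. Section 9 says only that replaced patients remain evaluable for safety and toxicity.
- That any chronic GVHD with onset by 1 year counts, because the endpoint wording could be read as status at 1 year.
- Whether Cohort B has 26 patients, as in its decision rule, or 27, as in the accrual estimate and the Protocol Summary.

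Then add to Section 9, as an exception to the sentence on interim analysis:

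*Enrolment to a cohort closes when the 10th (Cohort A) or 13th (Cohort B) patient among those who count toward the final 25 or 26 has confirmed chronic GVHD with onset within 1 year of HCT; the cohort is then concluded ineffective, and patients already enrolled complete follow-up.*

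State that this curtails the existing rule and leaves type I error and power unchanged. The text governs enrolment only.

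The cost is a running case count. In a failed cohort there would also be a few patients fewer for the incidence interval, safety and secondary estimates, and about 1 percentage point of upward bias in the reported chronic GVHD rate at the null, which the report should mention.

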- Unexplained immunologic graft rejection at day +90 (± 7 days) (define as donor myeloid-cell chimerism of <5%)
- Grade 4 neutropenia ($ANC <500/\text{mm}^3$) lasting ≥ 14 consecutive days, (definitely or probably) related to MLN9708
- Grade 3 neutropenia with fever and/or infection, where fever is defined as a temperature $\geq 38.5^\circ\text{C}$, (definitely or probably) related to MLN9708
- Grade 4 thrombocytopenia (platelets $<25,000/\text{mm}^3$) lasting at least 7 consecutive days, (definitely or probably) related to MLN9708

- The phase II portion will utilize the MTD for MLN9708, determined from phase I portion of the study. In phase II, patients will be enrolled in two independent cohorts of matched sibling and matched unrelated donor transplants.

- During the phase II portion, for chronic GVHD prophylaxis, four doses of MLN9708 will be administered orally on days 1, 8, 15 and 22, starting on day +60 to +90 post allogeneic HCT.
- All protocol-specific criteria for administration of study drug must be met and documented before drug administration. Study drug will be administered or dispensed only to eligible patients under the supervision of the investigator or identified sub-investigator(s). Patients should be monitored for toxicity, as necessary.
- Capsules of MLN9708 will also be referred to as study drug. Study drug will be supplied by Millennium as capsules of 2.3, 3.0 and 4.0 mg MLN9708.
- Patients should be instructed to swallow MLN9708 capsules whole, with water, and not to break, chew, or open the capsules. Study drug should be taken on an empty stomach (no food or drink) at least 1 hour before or 2 hours after a meal. Each capsule should be swallowed separately with a sip of water. A total of approximately 8 ounces (240 mL) of water should be taken with the capsules.
- All MLN9708 doses will be administered by authorized study personnel during patients' inpatient or outpatient visits, to ensure compliance. If the patient vomits after taking the study drug, the dose should not be repeated but should resume dosing at the time of the next scheduled dose. Missed doses can be taken as soon as the patient remembers if the next scheduled dose is 72 hours or more away. A double dose should not be taken to make up for a missed dose.
- Acute GVHD medications expected to be ongoing at the time of MLN9708 administration include calcineurine inhibitors (e.g. tacrolimus or cyclosporine) OR mycophenolate mofetil OR sirolimus OR atorvastatin.

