- Tapering of any concomitant acute GVHD prophylaxis will be per institutional guidelines, however in absence of acute GVHD, renal insufficiency and disease relapse/progression it is recommended that taper **SHOULD NOT** commence before day +100. The recommended goal of tapering is the complete discontinuation of immunosuppressive medications by day +180.

Excluded Concomitant Medications and Procedures

The following medications and procedures are prohibited during the study:

Systemic treatment with any of the following metabolizing enzyme inhibitors is not permitted during this study. A DDI with a strong inhibitor would increase MLN2238 exposure.

- Concomitant administration of strong inhibitors of CYP1A2 (fluvoxamine, enoxacin, ciprofloxacin) and strong inhibitors of CYP3A (clarithromycin, telithromycin, itraconazole, voriconazole, ketoconazole, nefazodone, and posaconazole).

Systemic treatment with any of the following metabolizing enzyme inducers should be avoided unless there is no appropriate alternative medication for the patient to use. A DDI with a strong inducer would decrease MLN2238 exposure.

- Strong CYP3A inducers (rifampin, rifapentine, rifabutin, carbamazepine, phenytoin and phenobarbital).
- The dietary supplements St. John's wort and Ginkgo biloba are not permitted.
- Antibiotic prophylaxis will be given according to institutional guidelines. Herpes zoster prophylaxis per institutional guidelines will be required during prophylaxis with MLN9708.
- Patients missing a single dose of MLN9708 (due to decreased oral intake secondary to severe nausea, vomiting, mucositis etc.) should be discussed with study PI. Patients missing >1 dose will need to be replaced. In case MLN9708 therapy is interrupted, the time interval should be recorded.
- Toxicity will be evaluated according to CTCAE v4.0.
- Progression free survival (PFS) and overall survival (OS) following transplantation will be recorded.

Dose modification

- Patients experiencing a grade 3-4 hematological or non-hematological toxicity (as specified in CTCAE v4.0) thought to be related to MLN9708 will be removed from the study permanently (except the exceptions allowed in Table 3). No dose modifications are permitted.

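### The go/no-go counts chronic GVHD cases over a fixed 25 or 26, while the planned estimate is a 1-year cumulative incidence; patients of unknown status make the two diverge, and the count as worded favours a promising verdict

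*Combined protocol and SAP*

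**What the plan says.** All of the decision text is in section 9, Statistical Considerations.

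- **Decision.** For siblings, "if 10 or more of 25 patients have chronic GVHD, we will conclude the new treatment is ineffective in Cohort A". For unrelated donors the same rule applies at 13 or more of 26. The error rates come from an exact binomial calculation, which gives every patient a yes/no outcome.
- **Endpoint label.** "The efficacy endpoint is chronic GVHD-free at 1 year".
- **Estimate.** "The chronic GVHD rate at 1-year and its 95% CI will be calculated by cumulative incidence method, while accounting for competing events". On competing events, "those for chronic GVHD are relapse or death without chronic GVHD". This matches the phase II primary objectives, which are worded as 1-year cumulative incidence from transplant.
- **Replacement.** Section 5 says "Patients missing >1 dose will need to be replaced". Section 9 says "Patients replaced on the protocol (as specified in the Dose Modification Section) will remain evaluable for safety and toxicity assessment". The Dose modification text in section 5 describes removal, not replacement: patients with grade 3-4 toxicity "thought to be related to MLN9708 will be removed from the study permanently", apart from the Table 3 exceptions.
- **Timing.** Phase II doses are given "on days 1, 8, 15 and 22, starting on day +60 to +90 post allogeneic HCT". GVHD is assessed about weekly to day +100, then at each study visit (days 180 and 365 within the first year).
- **Number.** The Cohort B rule is written for 26; the Protocol Summary and the Accrual Estimate enrol 27.

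**The concern.** The plan does not say how a patient without a known 1-year status enters the count, or whether the count or the cumulative incidence governs if they disagree. Read as worded, the rule counts patients who have the disease, so someone lost before onset adds nothing to the numerator but stays in the 25 or 26. That pushes towards a promising verdict. The planned estimator would censor the same patient.

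The count is also silent on chronic GVHD that appears after relapse. The estimator is not, because relapse is a competing event there.

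The denominator is open too. Replaced patients stay evaluable for safety, but their efficacy status is not given, and the section cited for replacement contains no replacement rule. At these sample sizes one patient shifts the error rates visibly. In an open-label trial, an unwritten scoring rule could be chosen after outcomes are known.

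**Working it through.** **1. The plan's own figures.** Inputs from section 9: A has n = 25, promising at 9 or fewer cases, null 55%, alternative 30%. B has n = 26, promising at 12 or fewer, null 65%, alternative 40%. X is the number of cases, binomial.

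| | Type I error | Stated | Power | Stated |
|---|---|---|---|---|
| A: P(X ≤ 9; n = 25) | 0.0440 | 0.04 | 0.8106 | 0.80 |
| B: P(X ≤ 12; n = 26) | 0.0377 | 0.05 | 0.8007 | 0.81 |

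A reproduces. B's power is within a point of the stated figure; its exact type I error is below the stated 0.05.

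**2. When count and incidence agree.** With no censoring, the cumulative incidence equals cases divided by n, because relapse and death without chronic GVHD stay in the denominator as non-cases. They diverge once someone is censored. For example, 9/25 = 36.0% is a go, but if three patients are censored before the first event the incidence is 9/22 = 40.9%, above the no-go fraction 10/25 = 40%.

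**3. One patient of unknown status per cohort, lost at entry (worst case).**

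- Scored as a non-case, type I error is P(X ≤ 9; 24, 0.55) = 0.0648 in A and P(X ≤ 12; 25, 0.65) = 0.0604 in B.
- Scored as a case, power is P(X ≤ 8; 24, 0.30) = 0.7250 in A and P(X ≤ 11; 25, 0.40) = 0.7323 in B. Type I error falls to 0.027 and 0.025.

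**4. Loss spread over follow-up.** The documents give no rate, so 5% and 10% are assumptions. Simulation used constant cause-specific hazards giving the null 1-year rates, competing events of 15% or 25%, and independent loss, exponential or uniform. Type I error with non-case scoring:

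| Assumed loss | A | B |
|---|---|---|
| 5% | about 0.055 | about 0.05 |
| 10% | about 0.068 | about 0.063 |

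**5. A limit that matches the cut-offs.** Let F be the 1-year incidence and S = 1 − F. The upper limit is 1 − exp{ln(S) × exp(z × se)}, with se = √Var(F) / (S × |ln S|). With complete follow-up Var(F) = F(1 − F)/n; z = 1.645 for a two-sided 90% interval.

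For 9/25: S = 0.64, √Var = √(0.36 × 0.64/25) = 0.096, |ln S| = 0.4463, se = 0.096/(0.64 × 0.4463) = 0.336. The limit is 1 − exp(−0.4463 × e^0.553) = 0.540.

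| Cases | 90% upper limit | Null | Result |
|---|---|---|---|
| 9/25 | 54.0% | 55% | promising |
| 10/25 | 57.9% | 55% | ineffective |
| 12/26 | 63.3% | 65% | promising |
| 13/26 | 66.8% | 65% | ineffective |

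The planned 95% interval would not reproduce the rule: its upper limits are 57.8% at 9/25 and 66.7% at 12/26. In the simulation, the 90% rule holds type I error near 0.037 under 5-10% spread loss.

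**6. If 27 unrelated-donor patients are analysed.** At most 12 of 27 gives type I error 0.023 and power 0.750; at most 13 gives 0.054 and 0.855. The 90% limit at 13/27 is 64.8%, so the interval rule would pass 13.

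**The case against.** The null is stated as a 1-year chronic GVHD rate, and section 9 says that rate is calculated by cumulative incidence. Count and estimate therefore target the same quantity and coincide under complete follow-up. This stands: a reader might infer that the two are unrelated, and the documents do not support that.

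Unknowns may be few. GVHD is checked weekly to day +100, visits follow at days 180 and 365, and death and relapse are known outcomes. This also stands. No document figure supports any particular loss rate, and a mild one leaves Cohort B at its stated 0.05.

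The one-patient figures assume loss at entry. A patient lost event-free late in the year would probably have been a non-case anyway. A patient lost before the third dose misses more than one dose and falls under the replacement rule. So those figures are an upper bound per patient lost, not a typical effect.

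A reader might take the chronic GVHD-free label to mean that an unknown status counts as a failure, and infer a serious loss of power. That is the less natural reading: the rule counts patients who have the disease, and no sentence scores an unobserved patient as a case. That scoring would also lower type I error. Nor do the documents say that GVHD follow-up stops on removal; they leave it unstated.

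Finally, a confidence-limit rule replaces an exact test with an asymptotic one. That is a fair cost, but it does not remove the need to say how unknowns are scored.

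**Conclusion.** The concern holds in a limited form. The decision rule and the planned estimate treat a patient of unknown 1-year status differently, and the rule as worded leans towards a promising verdict. With complete status, and chronic GVHD after relapse not counted, there is no discrepancy.

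The inflation is modest under mild loss. Cohort A goes from 0.044 to about 0.055 at an assumed 5%, and Cohort B from 0.038 to about 0.05. At 10% both exceed their stated levels. The 0.065 and 0.060 figures are worst cases for one patient per cohort. All of the spread-loss figures rest on assumed rates and on loss independent of chronic GVHD risk.

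The unclear efficacy denominator, and 26 against 27 in Cohort B, are gaps in the text whatever the loss rate. The plan should be amended, but its stated error rates are not invalid if follow-up is complete.

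**What to change.** 1. **Decision.** State that it rests on the planned 1-year cumulative incidence, with relapse and death competing and losses censored. A cohort is promising if the upper limit of the two-sided 90% confidence interval, complementary log-log on 1 minus the incidence, is below 55% (A) or 65% (B). Name the interval type: a log(−log) limit on the incidence itself gives 64.7% at 13/26 and would move Cohort B's cut-off. If the exact count is kept, the minimum is to state how unknown status and post-relapse chronic GVHD are scored, and to report the decision with unknowns scored both ways.
2. **Denominator.** State that chronic GVHD status is still recorded to 1 year for removed and replaced patients. Reconcile sections 5 and 9 on who is replaced, and define who is in the efficacy analysis. Report how many patients have unknown 1-year status.
3. **Cohort B.** Settle 26 or 27 first, then restate the cut-off and error rates.

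**Cost.** A protocol amendment that changes the primary decision rule but adds no procedures. The limit is asymptotic at 25-26 patients, and censoring assumes losses are unrelated to chronic GVHD risk. The decision is no longer a simple count when follow-up is incomplete. Power falls to about 0.76 (A) and 0.77 (B) with 10% loss, from 0.81 and 0.80 with none.
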